### 3.7 Management of Treatment Failures

Treatment failures (as determined by the site investigator at the time of CDI recurrence) are to be treated with the therapy(ies) deemed most appropriate by their study investigator. All CDIs, including reoccurrences and new episodes, are to be captured in detail on the CDI History and On-study Episodes eCRF.

### 3.8 Determination of Treatment Success/Failure

The site investigator makes the determination of success based on: the absence of CDI diarrhea without the need for retreatment with *C. difficile* anti-infective therapy or FT < 56 days after completion of study treatment. S/he makes the determination of failure based on the four criteria for treatment failure listed in Section 3.6, above.

### 3.9 Blinding

This is an open-label study; no blinding will be employed.

## 4.0 Treatment Subject Selection and Withdrawal

### 4.1 Inclusion Criteria

All responses must be “yes” to include a subject in the study:

1.  $\geq 18$  years old.
2. Medical record documentation of recurrent CDI including a positive *C. difficile* test within 60 days prior to enrollment and either: a) at least two recurrences after a primary episode and has completed at least two rounds of standard-of-care oral antibiotic therapy or b) has had at least two episodes of severe CDI resulting in hospitalization.
3. Already taking or will start a course of antibiotics to control recurrent CDI symptoms at the time of enrollment. [REDACTED]

4. Willing and able to have an enema(s).
5. Willing and able to complete the stool and serum testing required for the study.

6. [REDACTED]
- [REDACTED]
- [REDACTED]
- [REDACTED]
- [REDACTED]
- [REDACTED]
- [REDACTED]
- [REDACTED]
- [REDACTED]
- [REDACTED]

10. [REDACTED]
11. Willing to complete the required Subject Diary.
12. Willing and able to meet all study requirements, including completing the assessment visit and phone calls.

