**3.6 Definition of Treatment Failure**

Treatment failure (CDI recurrence) is defined as: 1) the presence of CDI diarrhea (see Section 3.4), with or without other CDI symptoms,  $< 56$  days after completion of study treatment; 2) a positive stool test for *C. difficile*; 3) need for retreatment for *C. difficile* infection; and 4) no other cause for CDI symptoms has been determined. [REDACTED]

[REDACTED]

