#### 4.3 Subject Recruitment and Screening

Subjects are recruited by qualified and trained site personnel when they are identified as experiencing either a) at least two recurrences of CDI after a primary episode (i.e., at least three episodes) and have completed at least two rounds of standard-of-care oral antibiotic therapy or b) had at least two episodes of severe CDI resulting in hospitalization. Potential subjects are to be fully informed as to this study's purpose, requirements, anticipated risks, etc., and are to be given the chance to review the informed consent form and receive satisfactory answers to all questions. Subjects must then sign the study-specific, IRB/REB-approved Informed Consent Form and HIPAA Form (if applicable), which is the point of study enrollment.

Subjects are eligible to receive study treatment upon confirmation that they have met all inclusion/exclusion criteria listed in Sections 4.1 and 4.2. Subjects must discontinue their antibiotics for 24-48 hours prior to receiving the first study enema.

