4 STUDY DESIGN

4.1 General Design

This is a prospective, multicenter, open-label study assessing the efficacy and safety of RBX2660 as an adjunct to antibiotics for the treatment of recurrent CDI. Up to approximately 150 subjects will be enrolled in this study and receive RBX2260. Approximately 100 historical controls will be chosen from a retrospective chart review of patients treated with antibiotics for recurrent CDI who match key inclusion/exclusion criteria from the study.

Subjects who meet all inclusion and exclusion criteria, including having a positive *C. difficile* test within 60 days prior to enrollment and experiencing either a) at least two recurrences after a primary episode (diagnosis must include at least one positive *C. difficile* test on record within 60 days prior to enrollment) and have completed at least two rounds of standard-of-care oral antibiotic therapy or b) have had at least two episodes of severe CDI resulting in hospitalization prior to enrollment, will receive open-label treatment with RBX2660. One study treatment consists of two RBX2660 enemas administered 7 ± 2 days apart; the second enema may be administered sooner if CDI diarrhea reoccurs in less than 7 days. Subjects will already be taking or will start a course of antibiotics to control recurrent CDI diarrhea at the time of enrollment, [REDACTED]

[REDACTED] An in-office follow-up visit will occur at 8 weeks after completing study treatment for the assessment of AEs, efficacy, collection of the Subject Diary, and blood tests. Telephone assessments for AEs including serious adverse events (SAEs) and the new onset of chronic diseases and CDI symptoms will occur at weeks 1, 2, 3, and 4 and at 3, 6, and 12 months after completing study treatment. Assessment of serious adverse events and the new onset of chronic diseases will occur via phone call at 24 months after completing study treatment. Subjects will keep a detailed Subject Diary to assess for solicited adverse events from the date of enrollment to one week after completing study treatment (second enema). Treatment

failures (as determined by the site investigator at the time of CDI recurrence) are eligible to receive another therapy deemed most appropriate by their study investigator.

[REDACTED]

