4.2 Discussion of Study Design

Screening will be performed before treatment and will include demographics, a complete medical history, a review of inclusion/exclusion criteria, stool and blood testing, a modified physical exam, Form SF-36 completion, vital signs, Subject Diary recording, and urine pregnancy test for all females of childbearing potential.

The target population is adults (≥ 18 years old) with recurrent CDI who have had either a) at least two recurrences after a primary episode [REDACTED] and have completed at least two rounds of standard-of-care oral antibiotic therapy or b) have had at least two episodes of severe CDI resulting in hospitalization.

For study entry, recurrent CDI is defined as a documented diagnosis of recurrent CDI (recurrence of CDI symptoms for at least two consecutive days that begins less than 8 weeks after completion of CDI treatment) and at least one positive stool test for the presence of *C. difficile* on record within 60 days prior to enrollment.

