8.3 Baseline Assessments

Baseline assessments are collected within 30 days before study treatment administration. Summaries for age (years), sex, ethnicity, and race will be provided for the Full Analysis Set. Baseline BMI and employment status will also be summarized. *C. difficile* infection history will be summarized by total number of episodes and by each episode. The following will be summarized for each episode of CDI: duration (days), treatment administered, hospitalization with duration (if applicable) and available *C. difficile* test results.

For Form SF-36, the results obtained at the Screening visit will be used for the baseline assessment.

[REDACTED]

- [REDACTED]
- [REDACTED]
- [REDACTED]
- [REDACTED]
- [REDACTED]
- [REDACTED]

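### The qualifying C. difficile test is not tied to the current episode, and controls face a different, looser test rule, so proof of disease at entry differs between the groups with unknown net bias.

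*Protocol*

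**What the plan says.** **RBX2660 entry.** Inclusion 2 (Protocol 4.1, repeated in the synopsis) asks for documented recurrent CDI with a positive *C. difficile* "test within 60 days prior to enrollment and either: a) at least two recurrences after a primary episode", or route b for severe episodes with hospital admission. The look-back ends at consent, "which is the point of study enrollment" (Protocol 4.3).

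**SAP entry definition.** Protocol 3.3 is redacted, but SAP 4.2 gives a readable study-entry definition: symptoms returning for at least two days in an episode "that begins less than 8 weeks after completion of CDI treatment", plus at least one positive "stool test for the presence of *C. difficile* on record within 60 days prior to enrollment". SAP 4.1 says that the diagnosis must include at least one positive "test on record within 60 days prior to enrollment) and have completed at least two rounds of standard-of-care oral antibiotic therapy". None of these names the episode that the test must belong to.

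**Outcome.** Failure (Protocol 3.6) needs four things together: CDI diarrhea, "2) a positive stool test for" *C. difficile*, need for retreatment, and no other cause. Success (Protocol 3.5) needs no test, and Protocol 6.8 classes a subject without CDI reoccurrence before day 56 as a success.

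**Controls.** Appendix 1, A6.1 requires at least one positive test at original diagnosis, with no limit on its age. A4 likewise asks only for one positive test on record.

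**The concern.** The 60-day window is longer than the 8-week interval that defines a recurrence. A test from the previous, already treated episode can therefore satisfy inclusion 2 while the current episode has no laboratory confirmation. Failure, by contrast, cannot be declared under Protocol 3.6 without a positive test. A subject whose presenting diarrhea had another cause could enter without proof of CDI and leave as a success for want of it, whatever RBX2660 did.

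The primary analysis is open-label and non-randomized, and Appendix 1, A2 aims for a closely matched control set. If the two groups enter on different proof of disease, part of any difference in recurrence-free rates may reflect who was let in.

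**Working it through.** The plan states no figure on this point. Its sample size (up to about 150 RBX2660 subjects and about 100 controls, SAP 4.5) is not in dispute, and the assumptions behind it are redacted.

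**1. Can the previous episode's test qualify?**

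Document inputs: 60-day look-back from consent; recurrence less than 56 days after treatment ends. Assumptions: T days from the previous test to the end of that treatment; onset spread evenly over the 56 days; L days from onset to consent. The old test is in date if T + t + L ≤ 60, where t is the number of days from end of treatment to onset. The share of recurrences it covers is (60 − T − L)/56.

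| T | L | Latest t | Share |
|---|---|---|---|
| 10 | 3 | 47 | 47/56 = 84% |
| 10 | 7 | 43 | 43/56 = 77% |
| 10 | 14 | 36 | 36/56 = 64% |
| 14 | 3 | 43 | 43/56 = 77% |
| 14 | 7 | 39 | 39/56 = 70% |
| 14 | 14 | 32 | 32/56 = 57% |

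Example: test on day −60, treatment ends on day −50, symptoms return on day −7 (43 days later), no new test, consent on day 0. All readable entry wording is met. The route closes only for long T with long L: T = 42 and L = 21 gives 60 − 63 = −3.

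**2. Does another step close the route?**

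- Screening stool is requested for the sponsor (Protocol 6.4.1), and baseline stool is tested for baseline health (6.5). Neither is a visible condition of entry.
- The Per Protocol set (SAP 6.3) removes eligibility violations, but these subjects violate no readable criterion.
- The readable analyses in SAP 8.7.1 and subgroups in SAP 7.8 do not separate them.

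**3. Effect on the RBX2660 rate**

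Observed rate = (1 − f)p + f·s, where p is the true success rate, f the share whose current episode is not CDI, and s their success rate. The rise is f(s − p). All three inputs are assumptions, except that p = 0.35 follows from the 65% recurrence after two relapses in Appendix 1, A3.

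- p = 0.70, with 20% to 50% of the arm untested in the current episode and 10% to 30% of those without CDI, so f = 0.02 to 0.15. With s = 1: 0.02 × 0.30 = 0.6 points to 0.15 × 0.30 = 4.5 points. With s = 0.9: 0.02 × 0.20 = 0.4 to 0.15 × 0.20 = 3.0 points.
- p = 0.35, f = 0.10: 0.90 × 0.35 + 0.10 × 0.9 = 0.405; with s = 1, 0.415.

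**4. Effect on the comparison**

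Take no true difference (0.35 in both groups), 150 against 100, an assumed two-sided 5% level, pooled-variance normal approximation, and s = 0.9 to 1.0. The chance of a significant result favouring RBX2660 is:

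| f in RBX2660 arm | Controls 0 | Controls f | Controls 2f |
|---|---|---|---|
| 5% | 6–7% | 2.5% | below 1% |
| 10% | 14–17% | 2.5% | below 1% |
| 20% | 41–53% | 2.5% | below 1% |

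The direction depends on the control share, which the documents do not give.

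**The case against.** **Redaction.** Protocol 3.3 is blacked out, as are parts of the inclusion list, the Visit 1 and screening-stool text, and the SAP schedule. A link could sit there. This stands as a limit, but the readable definition in SAP 4.2 has no link.

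**The wording already ties test to diagnosis.** Inclusion 2 makes the test part of the documentation of recurrent CDI, and SAP 4.1 makes it part of the diagnosis. So a clinical diagnosis of recurrence is still needed. What is not required is laboratory proof from the current episode.

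**Existing filters.** Protocol 4.2 excludes known continued diarrhea on CDI antibiotics, IBD, IBS, chronic diarrhea, celiac disease and other confirmed pathogens. These reduce the number of mislabelled subjects but do not remove the route.

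**Success is not automatic.** A reader might infer that these subjects are certain successes. The documents do not support that. CDI diarrhea is defined by stool count and duration alone (Protocol 3.4), so returning diarrhea of another cause does not plainly meet the success definition. Retreatment can be decided without a positive test (6.8). These subjects also remain at risk of true recurrence.

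**The controls.** A reader might infer bias in favour of RBX2660. The looser control rule blocks that inference, because mislabelled control episodes could offset or reverse the effect. It does not remove the point: the test rules differ, and neither is linked to the episode.

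**Conclusion.** The point stands on the readable text: an RBX2660 subject can qualify on the previous episode's test, and controls qualify on a test from original diagnosis. Proof of disease at entry is therefore unequal and not episode-linked in either group.

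The likely effect within the RBX2660 arm is upward, 0.4 to 4.5 points under the assumed shares with p = 0.70; the lowest value is under one subject in 150 (0.004 × 150 = 0.6). The net bias in the primary comparison is of unknown direction and size.

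The 57% to 84% should not be read as the share of subjects entering untested. It is the share of recurrences for which an old test would still be in date, under the assumed course lengths, delays and even spread of onset. How often no new test was done has to come from the trial's own data.

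**What to change.** Add to SAP 8.7.1 a sensitivity repeat of the primary comparison, limited to RBX2660 subjects and controls with a positive test dated within the qualifying episode. Define that episode in the same way for both groups. Report per group the number excluded and the number with no available test for that episode. Episode histories and test results are already collected (SAP 8.3; Appendix 1, A4), although SAP 8.3 promises only the available results.

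The cost is one definition and one table, and a wider interval. The loss of controls could be sizeable, since their rule never asked for a recent test. For illustration, if 50 of 100 controls remained, the 95% half-width around a control rate of 0.35 would grow from 1.96 × √(0.35 × 0.65/100) = 9.3 points to 1.96 × √(0.35 × 0.65/50) = 13.2 points. For that reason it should stay a sensitivity analysis.

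Optionally, for subjects not yet enrolled, inclusion 2 (with the synopsis and SAP 4.1 and 4.2) could require the test to come from the current episode. The trade-off is enrollment: patients treated without a new test would become ineligible. If the redacted Protocol 3.3 already contains the link, SAP 4.2 should be aligned with it; the different rule for controls would remain.

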#### 4.2 Exclusion Criteria

All responses must be “no” to include a subject in the study:

1. A known history of continued CDI diarrhea despite being on a course of antibiotics prescribed for CDI treatment.
2. Requires continuous antibiotic therapy for a condition other than CDI.
3. Previous successful (resolution of CDI diarrhea) fecal transplant for recurrent CDI < 6 months prior to study enrollment.
4. Previous unsuccessful (recurrent CDI diarrhea was unresolved) fecal transplant.
5. Previous treatment with RBX2660.
6. Diagnosis of inflammatory bowel disease (IBD), e.g., ulcerative colitis, Crohn’s disease, or microscopic colitis.
7. Diagnosis of irritable bowel syndrome (IBS) as determined by Rome III criteria.
8. History of chronic diarrhea.
9. History of celiac disease.
10. Disease symptoms caused by a confirmed intestinal pathogen other than *C. difficile*.
11. Colostomy.
12. Intraabdominal surgery within the last 60 days.

[REDACTED]

[REDACTED]

[REDACTED]

[REDACTED]

[REDACTED]

[REDACTED]

[REDACTED]

[REDACTED]

18. Life expectancy of < 12 months.
19. Compromised immune system [REDACTED]
- [REDACTED]
- [REDACTED]
- [REDACTED]
- [REDACTED]
- [REDACTED]
- [REDACTED]
- [REDACTED]
- [REDACTED]
- [REDACTED]

[REDACTED]

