**A2. Objective**

The objective of the antibiotic-treated historical control is to obtain a closely matched data set of the standard of care antibiotic treatment for recurrent CDI comparison to provide an adequate and well-matched set of data for the efficacy analysis of RBX2660.

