#### **A4. Study Design and Methods**

This is a retrospective chart review of patients treated with antibiotics for recurrent CDI who match key inclusion/exclusion criteria from the clinical study (see below). Patients will not be contacted. A waiver of Informed Consent/HIPAA authorization for the collection of chart data will be obtained from each site's IRB prior to beginning the chart review process. Site personnel will review their patient databases and identify patients with a diagnosis of multi-recurrent CDI, which is defined as a documented diagnosis of the return of CDI diarrhea ( $\geq 3$  watery stools in  $\leq 24$  hours for at least two consecutive days) that begins less than 8 weeks after completion of a CDI treatment regimen that resulted in the cessation of CDI symptoms. The diagnosis must include at least one positive *C. difficile* test on record. The identified charts will be accessed by the designated qualified and trained chart reviewer at the site. All patient records

on the list will be reviewed and a log will be kept documenting the review and why a record was excluded from the final historical control data set.

Data collection includes:

- demographics (age at the time of the start of data collection, gender, race, ethnicity);
- pre-existing conditions;
- concomitant medications;
- CDI history including each episode's start/stop dates, signs/symptoms, treatment(s) received, outcomes, and CDI-related hospitalizations;
- Blood and stool test results;
- Vital signs;
- Adverse events as recorded in the chart. (see Section 7.0 of the study protocol for all definitions). Adverse events will be adjudicated for seriousness, severity, and causality by the site investigator at the time of data collection as best as possible given the description of the event in the medical record.

[REDACTED]

All data and records will be kept in strict confidentiality as required by law and as stated in Section 9.4 of the study protocol.

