**A6.2 Exclusion Criteria for Selection of Historical Control Group**

All responses must be “no” to include a record in the study:

1. A known history of continued CDI diarrhea despite being on a course of antibiotics prescribed for CDI treatment.
2. Required continuous antibiotic therapy for a condition other than CDI.
3. Previous successful (resolution of CDI diarrhea) fecal transplant for recurrent CDI < 6 months prior to the date the most recent sequence of multi-recurrent CDI began.
4. Previous unsuccessful (recurrent CDI diarrhea was unresolved) fecal transplant.
5. Previous treatment with RBX2660.
6. Diagnosis of inflammatory bowel disease (IBD), e.g., ulcerative colitis, Crohn’s disease, or microscopic colitis.
7. Diagnosis of irritable bowel syndrome (IBS) as determined by Rome III criteria.
8. History of chronic diarrhea due to causes other than *C. difficile*.
9. History of celiac disease.
10. Disease symptoms caused by a confirmed intestinal pathogen other than *C. difficile*.
11. Colostomy.
12. Intraabdominal surgery within 60 days prior to the date the most recent sequence of multi-recurrent CDI began.

[REDACTED]

[REDACTED]

[REDACTED]

[REDACTED]

[REDACTED]

[REDACTED]

[REDACTED]

[REDACTED]

[REDACTED]

[REDACTED]

[REDACTED]

18. Life expectancy of < 12 months at initiation of treatment for CDI.

19. Compromised immune system [REDACTED]

[REDACTED]

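### The 6-month look-back for a prior successful fecal transplant starts from enrollment in the RBX2660 arm but from the start of the recurrent sequence in the controls, so the arms differ by rule on transplant history

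*Protocol*

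**What the plan says.** Protocol 4.2 item 3 excludes treated subjects with an earlier successful "fecal transplant for recurrent CDI < 6 months prior to study enrollment", where success means that the CDI diarrhea resolved. Section 4.3 makes signing the consent form the enrollment date ("which is the point of study enrollment"). By then the subject already has a primary episode plus at least two recurrences, or at least two hospitalized severe episodes.

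For the historical controls, Appendix 1, A6.2 item 3 keeps the 6 months but counts them for a successful "fecal transplant for recurrent CDI < 6 months prior to the date the most recent sequence of multi-recurrent CDI began". The visible text does not say whether a sequence begins at the primary episode or at the first recurrence. Appendix 1, A4 defines the control diagnosis by a return of diarrhea "that begins less than 8 weeks after completion of a CDI treatment regimen that resulted in the cessation of CDI symptoms".

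Item 4 has the same wording in both lists and no time limit: "Previous unsuccessful (recurrent CDI diarrhea was unresolved) fecal transplant". A2 states that the control group is meant "to obtain a closely matched data set of the standard of care antibiotic treatment".

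**The concern.** The primary analysis compares a recurrence-free proportion in an open-label, single-arm cohort with the proportion in chart-review controls. Without randomization, the comparison depends on both groups passing the same entry filter. RBX2660 is prepared from human stool, and the sponsor already treats transplant history as an eligibility factor, so this is a natural variable on which the groups should be alike. Appendix 1, A3 also describes transplant use as widespread, so prior transplant is not a remote possibility.

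Nothing visible in the SAP repairs a mismatch created by the entry rules. The affected patients meet their own arm's criteria, so the Per Protocol exclusion for eligibility violations (SAP 6.3) does not remove them. The transplant exclusion in that section concerns transplants before the 8-week follow-up, not earlier history. The subgroups in SAP 7.8 do not include prior transplant.

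**Working it through.** The plan states no figure to reproduce here. The check compares the two windows as sets of dates.

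**Notation.** F is the date of the successful transplant, S the start of the recurrent sequence, and E entry (enrollment, or the corresponding date for a control). Six months is taken as 182.5 days, which gives 182 whole days.

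- RBX2660 item 3 excludes F when 0 < E − F < 6 months.
- Control item 3 excludes F when 0 < S − F < 6 months.

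**Where they part when E is later than S.**

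1. F between S − 6 months and E − 6 months: excluded as a control, admissible to RBX2660. Example: the sequence began 4 months before entry and the transplant was 8 months before entry. For RBX2660, 8 > 6, so item 3 does not exclude. For a control the transplant was 8 − 4 = 4 months before S, and 4 < 6, so it does.
2. F on or after S and less than 6 months before E: excluded from RBX2660 by item 3. Control item 3 does not apply, because the transplant was not before S.

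**Days of F excluded, by gap E − S.**

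| E − S (days) | Controls only | RBX2660 only | Both arms |
|---|---|---|---|
| 0 | 0 | 0 | 182 |
| 24 | 24 | 24 | 158 |
| 69 | 69 | 69 | 113 |
| 138 | 138 | 138 | 44 |
| 240 | 182 | 182 | 0 |

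Each one-sided zone equals E − S, capped at 182 days. It is zero only when the reference dates correspond.

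**Plausible gaps.** Assume treatment courses of c = 10 to 14 days (not in the documents) and symptom-free intervals of g = 2 to 55 days (the upper end follows from the 8-week rule; the lower is assumed). Time from S to the second recurrence:

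- S at the primary episode: 2 × (c + g), from 2 × (10 + 2) = 24 to 2 × (14 + 55) = 138 days.
- S at the first recurrence: c + g, from 10 + 2 = 12 to 14 + 55 = 69 days.

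Further recurrences, or time between the last recurrence and consent, lengthen the gap.

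**Does item 4 close zone 2?** It depends on the meaning of success.

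- *Literal parentheses.* A transplant that resolved diarrhea before a relapse is successful under item 3 and not unresolved under item 4. Such a control is admitted.
- *The trial's own 56-day standard* (Protocol 3.5). Relapse within 8 weeks makes the transplant unsuccessful, and item 4 excludes the patient in both arms. Relapse at 8 weeks or later starts a new sequence, so the transplant precedes S and control item 3 applies. Zone 2 is then essentially empty.

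Zone 1 survives either reading. If a transplant counts as a CDI regimen under the 8-week rule, F must be at least 56 days before S. Zone 1 then runs from day −182 to at most day −56, or 182 − 56 + 1 = 127 days. The 24- and 69-day gaps are unaffected, since their zones end at days −159 and −114.

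**The case against.** Controls have no enrollment date, so some substitute was unavoidable, and A4 promises only key criteria. That explains why a substitute was used, but not this one. A6.2 item 18 in the same list is judged at initiation of treatment for CDI, so a date tied to treatment start was available. Item 12 (abdominal surgery) has the same shift as item 3.

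Text is blacked out in A4, A6.2 and SAP 4.4 and 4.5, and SAP 5.1 says controls were matched on a number of baseline factors. An index date or a matching rule on transplant history could be in the hidden text. This limits the point to what is visible.

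The inside-sequence group may be empty under the 56-day standard. This stands, and that half of the point is conditional.

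A reader might infer that both mismatches favor RBX2660: its arm gains known responders to stool-derived treatment, and the controls gain hard-to-treat relapsers. The documents do not support this. Patients in zone 1 also relapsed after their transplant and went on to a further recurrent sequence, so their history can be read as favorable or unfavorable. No passage gives a prognostic effect for either group.

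**Conclusion.** The point holds as a mismatch of reference dates. By rule, the RBX2660 arm can admit patients with a prior successful transplant whom the control rule excludes. The reverse mismatch, for a transplant within the sequence, exists only if success means any resolution of diarrhea.

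Each zone is as long as E − S, capped at 6 months. The ranges of 24 to 138 and 12 to 69 days rest on assumed course lengths and intervals, and on where a sequence is taken to begin.

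The documents do not give the number of patients affected, and the direction and size of any bias cannot be determined from them. For scale only, if 2% to 10% of an arm were affected and their recurrence-free rate differed by 10 to 40 points, that arm's rate would move by 0.02 × 10 = 0.2 to 0.10 × 40 = 4 points, in either direction. Those shares and differences are assumptions. The case for correction is comparability in a non-randomized comparison, not a demonstrated bias.

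**What to change.** In A6.2 item 3:

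- Count the 6 months back from a defined control index date that corresponds to enrollment: the start of the antibiotic course analysed for that control. The visible text does not define this date, so the appendix must.
- State that any transplant given within the sequence counts.
- Give the same meaning of successful and unsuccessful in items 3 and 4 of both lists, either any resolution or the 56-day standard.

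SAP 5.1 describes the controls as already chosen, and their outcomes are in the charts. Reviewers unaware of each control's outcome should therefore re-apply the rule to every logged record, including those previously excluded. Log each change, and report the primary comparison with the controls as already selected as a sensitivity analysis.

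The cost is a short edit to Appendix 1 and a re-check of transplant dates. A4 already collects episode dates and treatments received and keeps a log of exclusions. A few controls may be dropped and a few may become eligible.
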